- Reduction of subcutaneous fat volume over the treated area as measured by ultrasound compared with Baseline.

*Note: no efficacy assessments will be done for Group 1 of Stage 1 study.

The reduction of subcutaneous fat thickness and subcutaneous fat volume over the treated area will be summarized with descriptive statistics. An estimate of the 95% CI for the mean reduction in subcutaneous fat thickness and corresponding p-value will also be provided.

The analysis set for the primary efficacy analysis is the ITT population. The primary analysis will be repeated using the PP population, as relevant. Exploratory analyses may be performed to assess differences between the dose levels.

Full details of all efficacy analyses will be provided in the SAP.

Stage 2

Primary efficacy endpoints to be analyzed in Stage 2 are:

- The proportion of subjects who lose at least 150 mL of subcutaneous fat as measured by ultrasound from Baseline to follow-up visits compared with placebo.

Secondary efficacy endpoints to be analyzed in Stage 2 are:

- The proportion of subjects who lose at least 200 mL of subcutaneous fat as measured by ultrasound from Baseline to follow-up visits compared with placebo.
- Number of treatments required to first occurrence of reducing at least 150 mL of subcutaneous fat volume over the treated area as measured by ultrasound in CBL-514 group
- Reduction of subcutaneous fat volume over the treated area as measured by ultrasound compared with placebo
- Reduction of subcutaneous fat volume over the treated area as measured by ultrasound compared with Baseline

For the primary endpoint, the proportion of subjects who lose at least 150 mL of subcutaneous fat will be summarized for CBL-514 and placebo, respectively, along with their 95% confidence intervals.

The analysis set for the primary efficacy endpoint is the ITT population. The primary analysis will be repeated using the PP population, as relevant. Exploratory analyses may be performed to assess differences between treatments.

All analyses will be performed without adjustment for multiple endpoints.

Full details of all efficacy analyses will be provided in the SAP.

TABLE OF CONTENTS

1.	TITLE PAGE	1
	INVESTIGATOR'S AGREEMENT	4
	PROCEDURES IN CASE OF EMERGENCY	5
2.	SYNOPSIS	6
3.	TABLE OF CONTENTS, LIST OF TABLES, AND LIST OF FIGURES	20
4.	LIST OF ABBREVIATIONS AND DEFINITIONS OF TERMS	28
5.	FACILITIES AND PERSONNEL	31
6.	BACKGROUND AND INTRODUCTION	32
6.1.	Introduction.....	32

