16.3. Efficacy

Efficacy will be analyzed in both Stage 1 and Stage 2 of the study.

16.3.1. Stage 1

Efficacy endpoints to be analyzed in Stage 1 are:

- Reduction of subcutaneous fat thickness as measured by ultrasound compared with Baseline

- Reduction of subcutaneous fat volume over the treated area as measured by ultrasound compared with Baseline.

*Note: no efficacy endpoints will be assessed for Group 1 of Stage 1 study.

The reduction of subcutaneous fat thickness and subcutaneous fat volume over the treated area will be summarized with descriptive statistics. An estimate of the 95% CI for the mean reduction in subcutaneous fat thickness and corresponding p-value will also be provided.

The analysis set for the primary efficacy analysis is the ITT population. The primary analysis will be repeated using the PP population, as relevant. Exploratory analyses may be performed to assess differences between the dose levels. Full details of all exploratory analyses will be provided in the SAP.

16.3.2. Stage 2

Primary efficacy endpoints to be analyzed in Stage 2 are:

- The proportion of subjects who lose at least 150 mL of subcutaneous fat as measured by ultrasound compared with placebo

Secondary efficacy endpoints to be analyzed in Stage 2 are:

- The proportion of subjects who lose at least 200 mL of subcutaneous fat as measured by ultrasound compared with placebo
- Number of treatments required to first occurrence of reducing at least 150 mL of subcutaneous fat volume over the treated area as measured by ultrasound in CBL-514 group
- Reduction of subcutaneous fat volume over the treated area as measured by ultrasound compared with placebo
- Reduction of subcutaneous fat volume over the treated area as measured by ultrasound compared with Baseline

For the primary endpoint, the proportion of subjects who lose at least 150 mL of subcutaneous fat will be summarized for CBL-514 and placebo, respectively, along with their 95% confidence intervals.

The analysis set for the primary efficacy endpoint is the ITT population. The primary analysis will be repeated using the PP population, as relevant. Exploratory analyses may be performed to assess differences between the dose levels.

All analyses will be performed without adjustment for multiple endpoints.

Full details of all efficacy analyses will be provided in the SAP.

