2.3 Endpoints

2.3.1 Primary endpoints

Stage 1:

- Safety and tolerability following single dose of CBL-514 as assessed by recording of TEAEs, laboratory assessments, vital signs, ECGs, physical examinations, and injection site assessment.

Stage 2:

- The proportion of subjects who lose at least 150 mL of subcutaneous fat as measured by ultrasound from Baseline to follow-up visits compared with placebo. [Time frame: Visit 2 (Baseline), Visit 6, and Visit 7]

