3.1 General Considerations

All data collected on the electronic case report form (eCRF) will be presented in the data listings and will be listed and sorted by treatment arm participant number and visit, where applicable. All descriptive summaries will be presented by treatment group and nominal visit/time point (where applicable).

Unless otherwise stated, the following methods will be applied:

- Continuous variables: Descriptive statistics will include the number of non-missing values (n), arithmetic mean, standard deviation (SD), median, minimum and maximum values.

The minimum and maximum values will be displayed to the same decimal precision as the source data, the arithmetic mean, SD and median values will be displayed to one more decimal than the source data for the specific variable.

95% Confidence Intervals (CIs), mean differences (among treatments and from baseline) and least-square (LS-Means) values will be displayed to one more decimal than the source data for a specific variable. P-values will be displayed to 5 decimal places.

The appropriate precision for derived variables will be determined based on the precision of the data on which the derivations are based, and statistics will be presented in accordance with the above mentioned rules.

- Categorical variables: Descriptive statistics will include counts and percentages per category. The denominator in all percentage calculations will be the number of participants in the relevant analysis population with non-missing data, unless specifically stated otherwise. Percentages will be displayed to one decimal place. Proportions will be displayed to 3 decimal places.

95% Confidence Intervals (CIs), difference in proportions, and other categorical parameters will be displayed to one decimal place for percentages. Proportions will be displayed to 3 decimal places. P-values will be displayed to 5 decimal places.

- Repeat/unscheduled assessments: Only values collected at scheduled study visits/time points will be presented in summary tables. If a repeat assessment was performed, the result from the original assessment will be presented as the result at the specific visit/time point. All collected data will be included in the data listings.
- Assessment windows: All assessments will be included in the data listings and no visit windows will be applied to exclude assessments that were performed outside of the protocol specified procedure windows.

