- A summary table presenting the number and proportion of subjects who lose at least 150mL and subjects who lose at least 200 mL of subcutaneous fat volume over the treated area together with two-sided Clopper-Pearson 95% confidence intervals for each treatment group defined in section 3.7 will be produced.
- For the subcutaneous fat volume as measured by ultrasound data, summary statistics (as described in section 3.1) will be presented for values and change from baseline value at each visit.
- If the assumptions met, the Mixed-Effect Model Repeated Measurement (MMRM) will be used to assess the change over time in the CBL-514 and placebo treatment arms for the abdominal subcutaneous fat volume. The assumptions for MMRM can be checked as described in section 16.3. There will not be any alternative method used if assumptions of model-based analysis are not satisfied.

The model will include the following fixed factors/covariates:

- o Baseline subcutaneous fat volume,
- o Treatment Group,
- o Study Visit,
- o Treatment Group and Study Visit interaction term;

Subject as random effect and repeated visits will be also included in the model.

Unstructured within-subject covariance structure (TYPE=UN) will be selected for the model initially which makes no assumption about the relationship in the correlation among visits. If it leads to non-convergence, the following covariance structures will be explored: first order autoregressive (AR (1)), Heterogenous Toeplitz, Toeplitz, and compound symmetry, if appropriate. If the model does not converge, alternative covariance structures will be investigated. The Akaike Information Criteria (AIC) will be used to select the best model (smaller is better).

If model does not converge after the above, a standard regression model will be fitted at each time point using the same covariates as described above.

The Kenward-Roger (Kenward and Roger 1997) approximation will be used to estimate denominator degrees of freedom for tests of fixed effects.

Also, if the model is complex, simpler model will be explored.

The LS mean change from baseline, along with corresponding 95% CI and p-values for each treatment arm for Visit 3, Visit 4, Visit 5, Visit 6, and Visit 7 will be presented. In addition, the difference in change from baseline at Visit 6 and Visit 7 for CBL-514 600 mg versus placebo will be provided for the ITT population and repeated for PP Population.

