14.2 Efficacy

Table 14.2.1.1.i Summary of Abdominal Fat Thickness- Stage 1 (ITT Population)

Table 14.2.2.1.i Summary of Abdominal Fat Volume- Stage 1 (ITT Population)

Table 14.2.3.1.i Paired T-Test Results for Fat Thickness Change from Baseline- Stage 1 (ITT Population)

Table 14.2.4.1.i Paired T-Test Results for Fat Volume Change from Baseline - Stage 1 (ITT Population)

Table 14.2.2.2.i Summary of Abdominal Fat Volume- Stage 2 (ITT Population)

Table 14.2.2.2.ii Summary of Abdominal Fat Volume- Stage 2 (PP Population)

Table 14.2.5.2.i Summary of Subjects With At Least 150ml and 200ml Fat Volume Reduction from Baseline- Stage 2 (ITT Population)

Table 14.2.5.2.ii Summary of Subjects With At Least 150ml and 200ml Fat Volume Reduction from Baseline- Stage 2 (PP Population)

Table 14.2.6.2.i Statistical Analysis for Fat Volume Change from Baseline- Stage 2 (ITT Population)

Table 14.2.6.2.ii Statistical Analysis for Fat Volume Change from Baseline- Stage 2 (PP Population)

Table 14.2.7.2.i Summary of Treatments Required to First Occurrence Of At Least 150ml Of Fat Volume - Stage 2 (ITT Population)

Table 14.2.7.2.ii Summary of Treatments Required to First Occurrence Of At Least 150ml Of Fat Volume - Stage 2 (PP Population)

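### The 150 mL and 200 mL responder endpoints are defined against placebo, but no between-arm estimate or interval is prespecified for them

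*SAP*

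**What the plan says.** SAP section 2.3.1 defines the Stage 2 primary endpoint as the proportion losing at least 150 mL, "as measured by ultrasound from Baseline to follow-up visits compared with placebo", with Visits 6 and 7 as the follow-up time points. SAP section 2.3.2 words the 200 mL secondary endpoint the same way.

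The analysis given for both is in SAP section 10: a table of numbers and proportions, "together with two-sided Clopper-Pearson 95% confidence intervals for each treatment group defined in section 3.7 will be produced". (The treatment groups are in fact listed in SAP section 3.6.) Protocol section 16.3.2 agrees for the 150 mL endpoint: the proportion "will be summarized for CBL-514 and placebo, respectively, along with their 95% confidence intervals". The matching output in SAP section 17 is titled "Summary of Subjects With At Least 150ml and 200ml Fat Volume Reduction from Baseline- Stage 2 (ITT Population)", with a per-protocol counterpart.

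For mean fat volume, SAP section 10 goes further: "the difference in change from baseline at Visit 6 and Visit 7 for CBL-514 600 mg versus placebo will be provided", from the mixed model for repeated measures (MMRM).

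Three other places touch on a responder comparison:

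- SAP section 3.1 states that "difference in proportions, and other categorical parameters will be displayed to one decimal place for percentages".
- The protocol synopsis says, for Stage 2, "Exploratory analyses may be performed to assess differences between treatments". Protocol section 16.3.2 has instead "Exploratory analyses may be performed to assess differences between the dose levels".
- Protocol section 13.3 says the responder proportions are compared with placebo to judge significance. Protocol section 16 says there is no formal testing, and that the SAP prevails where the two diverge.

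**The concern.** The primary objective asks about a contrast between arms, and the planned output describes each arm separately. Two per-arm intervals do not show how precisely the contrast is estimated. The one planned placebo contrast is on mean volume, which is a different scale and a secondary endpoint.

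SAP sections 1 and 4 require analyses not identified in the SAP to be labelled post hoc in the study report. As written, the estimate that most directly answers the primary objective would carry that label, and its effect measure, interval method and visit would be open to choice after the data are seen. With a small placebo arm, the report could also omit how uncertain that estimate is.

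**Working it through.** **Step 1: is a between-arm responder analysis specified anywhere?**

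| Place | What it supplies |
|---|---|
| SAP 10, responder bullet | Proportion and interval per arm |
| Protocol 16.3.2 | The same, for 150 mL |
| SAP 17, Tables 14.2.5.2.i/.ii | Summary titles, no contrast named |
| SAP 3.1 | A decimal-place rule; no endpoint, visit, method or table |
| Synopsis and Protocol 16.3.2, optional analyses | Permission only, no method. The two wordings differ, and the dose-level wording does not fit Stage 2, which has one active group |
| SAP 10, MMRM | A placebo contrast, on mean volume |
| Protocol 13.3 | A significance statement with no test named and none in the SAP |

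None of these assigns an effect measure or a between-arm interval to either responder endpoint.

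**Step 2: sample sizes.** Protocol synopsis Table S3 and SAP section 2.5 give 50 and 25 randomized, with drop-out of 16% and 44%.

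- CBL-514: 50 × (1 − 0.16) = 42
- Placebo: 25 × (1 − 0.44) = 14
- Total: 42 + 14 = 56, which reproduces the planned evaluable number.

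Both 42 vs 14 and 50 vs 25 are used below. The SAP ITT set is all randomized subjects and early leavers are asked for an ultrasound, so the number with data may lie between the two.

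**Step 3: precision of the contrast.** The documents give no response rates, so the rates and counts here are assumptions. For arm i, let pᵢ = xᵢ/nᵢ with Wilson limits lᵢ and uᵢ, and let d = p₁ − p₂. The Newcombe 95% limits are

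- lower: d − √[(p₁ − l₁)² + (u₂ − p₂)²]
- upper: d + √[(u₁ − p₁)² + (p₂ − l₂)²]

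Example, 21/42 vs 2/14: d = 0.500 − 0.143 = 0.357. The Wilson limits are 0.355 to 0.645 and 0.040 to 0.399.

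- Lower: 0.357 − √(0.145² + 0.257²) = 0.063
- Upper: 0.357 + √(0.145² + 0.103²) = 0.535

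The difference is about 36 points (6 to 54). The Miettinen-Nurminen limits are 0.062 and 0.552, so the choice between the two methods matters little here. The planned output would show only 34 to 66% and 2 to 43%.

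At 25/50 vs 4/25 the difference is 34 points (Newcombe 11 to 50; Miettinen-Nurminen 11 to 52). The planned output would show 36 to 64% and 5 to 36%.

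**Step 4: expected width.** The mean Newcombe width, summed exactly over both binomial distributions:

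| Assumed true rates | 42 vs 14 | 50 vs 25 |
|---|---|---|
| 50% vs 15% | 47 points | 39 points |
| 60% vs 10% | 44 points | 36 points |
| 70% vs 5% | 40 points | 32 points |

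Even with a very large effect the interval is more than 30 points wide.

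**The case against.** The strongest reply is that the plan is consistent with its declared design. Protocol section 16 makes all analyses descriptive, and proportions set side by side are one way to compare with placebo. That stands as a reason not to ask for a test. It does not remove the gap: a difference with an interval is estimation, and the SAP already reports one for mean volume and labels the p-values exploratory.

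Second, the display rule in SAP section 3.1 may mean that a difference was intended, and the mock shells, which were not supplied, might contain one. That is possible, so the point is limited to the text and table titles.

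Third, a reader can subtract the two proportions and rebuild an interval from the counts. That is true, and no information is lost. What is missing is the prespecified method and the commitment to report it.

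Two stronger readings are tempting.

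- A reader might infer that overlapping per-arm intervals would make the trial look inconclusive. In both examples above they do overlap while the difference interval excludes zero. But neither document uses overlap as a decision rule, and whether it occurs depends heavily on the assumed counts: at 30/42 vs 1/14 the intervals are 55 to 84% and 0.2 to 34%, and they separate.
- A reader might infer from Protocol section 13.3 that a planned test is missing. The SAP contains no such test and prevails on divergence, so this is wording to reconcile and not a lost analysis.

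**Conclusion.** The point holds as a gap in prespecification. For the primary 150 mL and secondary 200 mL responder endpoints, the supplied text and table titles define a comparison with placebo but prespecify no between-arm effect measure or interval. Mean volume has such a contrast.

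The effect on reporting is that the contrast would be post hoc and its precision could go unreported. Under the assumed rates, the mean 95% interval width is about 40 to 47 points at 42 vs 14 and 32 to 39 points at 50 vs 25. These widths rest on assumed response rates and the planned sizes; they are not predictions.

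The documents do not support saying that the primary objective cannot be answered, that data are lost, or that a formal test is required. This is a nearly free improvement to an exploratory study.

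**What to change.** In SAP section 10 and Tables 14.2.5.2.i and 14.2.5.2.ii, add the CBL-514 minus placebo difference in proportions with a 95% Newcombe interval (or Miettinen-Nurminen; name one). Give it for both thresholds, at Visit 6 and at Visit 7, for ITT and PP, on the same denominator as the per-arm proportions, labelled exploratory. That is 2 thresholds × 2 visits = 4 extra rows in each of two existing tables.

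Add a sentence to the SAP saying that this estimate, without a significance test, replaces the significance wording of Protocol section 13.3. Since the SAP prevails, no protocol amendment is needed for this alone.

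Do not attach a row that counts missing subjects as non-responders. Missing data are a separate question: the SAP addendum removed imputation because the parties defined missing visits differently. Nor would the row be conservative when planned drop-out is 44% on placebo and 16% on CBL-514. In the example, 21/42 vs 2/14 becomes 21/50 vs 2/25, and the lower limit rises from 6 to 13 points.

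The cost is a few SAP sentences and minor table programming, with no new data and no change to the study's exploratory status.

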16.3 Appendix 3: MMRM Assumptions Testing

a) Sphericity assumption

The first assumption of the MMRM analysis is sphericity, posits that the repeated measures of a within-subjects effect should have equal variances and constant covariances.

- When the sphericity assumption is satisfied, the F-test in a standard analysis of variance is appropriate.
- When the sphericity assumption is violated, the F-test in a standard analysis of variance will be positively biased; that is, it will be more likely to make a Type I error (i.e., reject the null hypothesis when it is, in fact, true).
- Violation of sphericity was corrected using the Greenhouse–Geisser method.

b) Normality assumption

Kolmogorov-Smirnov normality test will be used to check normality of the data and the results will be presented.

SAS Proc to be used for normality testing:

```
ods output TestsForNormality = Normal;
proc univariate data=input normal plots;
var CFB; *CFB=Change from baseline;
histogram Diff /normal;
qqplot /normal (mu=est sigma=est);
run;
ods output close;
data Normality;
set Normal (where = (Test = 'Kolmogorov-smirnov'));
if pValue > 0.05 then Status = "Normal";
else Status = "Non-normal";
drop TestLab Stat pType pSign;
run;
```

Perform the following steps to check the normality of data.

1. First, check normality of data by pooling all visits data together if normality is achieved perform the parametric test.
2. If overall data doesn't show normality, check normality at each timepoint and if only few timepoints achieve normality, then still perform parametric test as normality can be assumed for non-normal timepoint.
3. If extreme outliers are present, then remove the outliers and check normality to perform parametric test.
4. Other normality tests result will be explored in case of departure from normality assumption.
5. If normality assumption is still violated, the normality will be assumed to perform parametric tests.

c) Test for Homoscedasticity

Homogeneity of variances between two treatment groups will be tested using Levene's test.

```
proc glm;  
class treat;  
model CHG = treat;  
means treat / hovtest=levene welch;  
  
run;
```

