Note that only the results from the HOVTEST= and WELCH options in PROC GLM account for variance heterogeneity. All other results assume equal variances. If heteroscedasticity occurs, all the results will be adjusted for unequal variances by adding the DDFM=SATTERTHWAITTE option in the MODEL statement to adjust the degrees of freedom for the unequal variances.

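### SAP section 10 and Appendix 16.3 conflict on whether a failed assumption check ends the MMRM, and the first check listed, sphericity, is not needed for the planned unstructured model

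*SAP*

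**What the plan says.** SAP section 10 (Efficacy, Stage 2) opens the model-based analysis with a condition: "If the assumptions met, the Mixed-Effect Model Repeated Measurement (MMRM) will be used to assess the change over time". It refers the checks to section 16.3 and then closes off any substitute: "There will not be any alternative method used if assumptions of model-based analysis are not satisfied". The model starts from TYPE=UN, "which makes no assumption about the relationship in the correlation among visits", with Kenward-Roger degrees of freedom in both the text and the sample code. If it does not converge, section 10 lists simpler covariance structures and finally a regression at each time point. Those fallbacks are for non-convergence, not for a failed assumption.

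Appendix 16.3 treats failed checks differently:

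- Sphericity: "The first assumption of the MMRM analysis is sphericity". Its remedy is "Violation of sphericity was corrected using the Greenhouse–Geisser method".
- Normality: after several steps, "If normality assumption is still violated, the normality will be assumed to perform parametric tests".
- Equal variances between arms: "If heteroscedasticity occurs, all the results will be adjusted for unequal variances", by putting the Satterthwaite option in the MODEL statement.

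**The concern.** Three things are wrong. First, section 10 says that a failed check leaves no analysis, while the appendix never reaches a point at which the MMRM is dropped. The SAP does not say which governs.

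Second, sphericity is a condition for the univariate F-test in repeated-measures ANOVA, which is the test the appendix's own bullets describe. Section 10 acknowledges that TYPE=UN makes no such assumption.

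Third, two remedies do not fit the planned model. Greenhouse-Geisser scales the degrees of freedom of the ANOVA F-test, which needs complete visit sequences; it does not act on visit-wise contrasts from PROC MIXED. Satterthwaite would replace the Kenward-Roger option that section 10 sets.

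At stake is the CBL-514 versus placebo difference in fat-volume change at Visits 6 and 7. No other between-arm efficacy estimate in the SAP has a specified method. The responder endpoints get a Clopper-Pearson interval for each arm, and section 3.1 mentions a difference in proportions only to set its decimals. Under protocol section 10.7 the sponsor is unblinded in Stage 2, so blinding does not protect a choice made after the data are seen.

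**Working it through.** **The two places side by side**

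| Check that fails | Section 10, read alone | Appendix 16.3 |
|---|---|---|
| Sphericity | No MMRM, no substitute | Greenhouse-Geisser, carry on |
| Normality | No MMRM, no substitute | Assume normality, carry on |
| Equal variances | No MMRM, no substitute | Satterthwaite, carry on |

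They disagree in every row.

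**Sample size used.** Protocol synopsis and SAP 2.5: 50 and 25 randomized, drop-out 16% and 44%. Evaluable = 50 × (1 − 0.16) + 25 × (1 − 0.44) = 42 + 14 = 56, which reproduces the plan's figure. The documents give no SD, correlation or effect size.

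**Simulation, illustrative only.** 42 versus 14 subjects; five post-baseline visits (Visits 3 to 7); complete normal data; no treatment effect; no baseline covariate; 20,000 runs per scenario. The SAP names no sphericity test, so Mauchly's test at 0.05 is an assumption, as are all covariances.

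- Mauchly: W = det(M) / (tr(M)/k)^k, where M is the pooled within-arm covariance of k = 4 orthonormal contrasts. The statistic is −f × 54 × ln W with f = 1 − (2k² + k + 2)/(6k × 54) = 1 − 38/1296 = 0.971, on k(k + 1)/2 − 1 = 9 degrees of freedom.
- Visit 7 test, unstructured: t = difference / √[s₇² (1/42 + 1/14)] on 54 degrees of freedom, with s₇² the Visit 7 variance. With complete data and no covariate this is what TYPE=UN gives.
- Visit 7 test, pooled: the same, with the variance averaged over the five visits and a normal reference, in the style of compound symmetry.

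| Assumed covariance | Mauchly rejects | Type I error, unstructured | Type I error, pooled |
|---|---|---|---|
| Compound symmetry 0.6, equal SDs | 4.8% | 0.050 | 0.053 |
| AR(1) 0.6, equal SDs | 99.1% | 0.051 | 0.053 |
| AR(1) 0.8, equal SDs | 100% | 0.048 | 0.051 |
| Compound symmetry 0.6, SD rising 1.5-fold | 35.4% | 0.049 | 0.101 |
| Compound symmetry 0.6, SD rising 2-fold | 86.5% | 0.052 | 0.137 |
| AR(1) 0.7, SD rising 2-fold | 100% | 0.049 | 0.131 |

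The simulation error near 0.05 is √(0.05 × 0.95 / 20,000) = 0.0015. The unstructured test holds its level whether or not sphericity holds, so the outcome of the check has no bearing on the validity of the planned contrast. The frequency of failure is set almost wholly by the assumed covariance.

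**The case against.** A reader might infer that a failed sphericity test removes the only between-arm efficacy estimate. That follows only from section 10 read by itself. No branch of Appendix 16.3 ends with the MMRM dropped, and the no-alternative sentence can be read to mean that no non-parametric substitute is used because the parametric model goes ahead. This stands: the documents support a contradiction, not a certain loss.

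A reader might also infer that the check is almost certain to fail because fat change accumulates over the courses. The documents give no covariance, test, significance level or pass mark for sphericity, and section 10 says only that the assumptions can be checked. The 99 to 100% rates belong to AR(1) patterns; compound symmetry with equal SDs gives 4.8%. This also stands.

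The stakes are limited too. The Stage 2 primary endpoint is the 150 mL responder proportion, and neither its table nor the per-arm summaries of change at each visit depend on the clause. The SAP treats the MMRM p-values as exploratory and supporting no claim. That lowers the severity, but an exploratory placebo contrast still needs a fixed rule for when it is reported.

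Finally, always fitting the unstructured model cannot mean ignoring non-convergence with about 14 evaluable placebo subjects. That is right, and the fallbacks must stay. They are not all harmless: the pooled column shows a Visit 7 type I error of 0.101 to 0.137 when the SD rises.

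**Conclusion.** The point holds as an internal contradiction with a misplaced check. Section 10 says a failed assumption ends the model-based analysis; Appendix 16.3 says it never does. Sphericity is irrelevant to the TYPE=UN model, Greenhouse-Geisser does not apply to its contrasts, and Satterthwaite conflicts with Kenward-Roger. The Visit 6 and Visit 7 difference is therefore reported, altered or omitted by a choice that the SAP leaves open until the data are seen.

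No stated figure is wrong. The simulated failure rate of 4.8% to 100% rests on Mauchly's test and assumed covariances and is not a forecast. That TYPE=UN does not need sphericity rests on the model itself and on section 10's own description of it. Because the analysis is secondary and exploratory, this is a should-fix.

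**What to change.** In SAP section 10, delete the opening condition on the MMRM and the sentence that rules out any alternative. State that the unstructured MMRM with Kenward-Roger is always fitted and its Visit 6 and Visit 7 contrasts always reported, with the existing non-convergence fallbacks retained, and that the report names the covariance structure actually used.

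In Appendix 16.3, delete part (a) and remove the Satterthwaite instruction in part (c). Keep the remaining diagnostics only to describe fit; they should not decide whether the model is run, which degrees-of-freedom method applies, or which observations stay in.

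The cost is SAP wording only: no new data and no change to sample size or visits. The lack of a specified between-arm estimate for the responder endpoints is a separate gap that this change does not close.
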